After completion of SBRT, the patients will then be re-evaluated for eligibility for continuation in the study and must have LAPC based on NCCN Guidelines as determined by review of CT, PET, or MRI imaging at our institution. Patients who have developed metastatic disease are no longer eligible to continue in the study. If the patients remain eligible for continuation in the study after rescreening, they will be assigned or randomized to a study arm (depending on when they were enrolled).

Due to availability of BMS-813160, study enrollment was closed as of December 19, 2022. Patients randomized prior to this will continue receiving study treatment as planned until drug supply expires on July 31, 2023, then will continue to receive any remaining study cycles without BMS-813160. Any patients who were enrolled but not randomized prior to December 19, 2022 (i.e. those receiving chemotherapy) will be assigned to a new arm (Arm C).

In phase I, the combination immunotherapy consists of nivolumab, CCR2/CCR5 dual-antagonist (BMS-813160) and GVAX. In phase II, the first 10 patients will be randomized 1:1 between Arm A and Arm B. Remaining patients will be assigned to Arm C.

Arm A subjects receive nivolumab and BMS-813160, Arm B subjects receive nivolumab, BMS-813160, and GVAX, and Arm C patients will receive nivolumab and BMS-813160 for Cycle 1 (prior to surgery) and then nivolumab and GVAX for Cycles 2 and beyond.

After randomization or assignment to a study arm, subject will receive Cycle 1 of the combination immunotherapy. Cycle 1 lasts 28 days and will start within two weeks of completion of SBRT.

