Further studies have shown the boosted effect of GVAX by its combination with low dose cyclophosphamide (Cytosan, CY) as an immune modulator. Tumors have several mechanisms for evading immune surveillance, including the development of tolerance with immunosuppressive regulatory T-cells.¹⁵⁻¹⁸ Murine breast cancer models treated with CY prior to vaccination showed an immune enhancing effect with suppression of Treg and increase in effector T-cells.¹⁹ In a phase II trial for treatment of Stage IV pancreatic cancer patients, the combination of CY/GVAX was noted to be safe and well-tolerated in gemcitabine-resistant metastatic pancreatic cancer, with grade 3/4 treatment-related events occurring in only one of 30 patients.²⁰ Median survival was 2.3 months versus 4.7 months in

A Phase I/II trial of combination immunotherapy with nivolumab and a CCR2/CCR5 dual antagonist (BMS-813160) with or without GVAX following chemotherapy and radiotherapy for locally advanced pancreatic ductal adenocarcinomas (PDACs)

patients receiving GVAX without and with CY, respectively. Pathologic evaluation revealed that there was a trend toward prolonged progression-free survival in patients who had persistent mesothelin-specific T-cell responses with immunotherapy.

In an ongoing neoadjuvant and adjuvant trial of CY/GVAX in patients with resectable pancreatic cancer (NCT01088789), pathological examination of PDAC tumor tissue resected just two weeks following a single neoadjuvant dose of GVAX identified the formation of novel vaccine-induced, immunologically active, tertiary lymphoid aggregates and organized lymph node-like structures, with suppression of the Treg pathway, that were not observed in tumor tissue resected from unvaccinated patients.²¹

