8.1 Tumor Tissue Studies

4-6 core tumor biopsies will be collected during

- 1) initial study enrollment if adequate diagnostic biopsy is not available,
- 2) the scheduled endoscopy with fiducial placement and
- 3) after pre-surgical evaluation if the patient is not a surgical candidate.

The core biopsy specimens will be collected for both snap frozen specimens and FFPE slides. The core formalin samples will be placed in one FFPE tissue block.

Additional tissue will be collected during surgical resection/NanoKnife procedure if the patient is a surgical candidate. Resected PDAs will be archived for FFPE tissue slides, frozen sections and freshly isolated TILs. Detailed instructions for tissue collection, processing and shipment are provided in the procedures manual.

The patient may also have biopsies of metastases performed. Post-treatment biopsies will only be obtained if the tumor is thought to be reasonably safe to biopsy, and biopsies not obtained due to concerns for patient safety will not be considered deviations. Additional optional biopsies may be obtained later in the course of therapy. Archival tumor samples will also be collected for every patient (slides and/or blocks). Archival tumor samples will not be

A Phase I/II trial of combination immunotherapy with nivolumab and a CCR2/CCR5 dual antagonist (BMS-813160) with or without GVAX following chemotherapy and radiotherapy for locally advanced pancreatic ductal adenocarcinomas (PDACs)

collected if the biopsy was a fine needle aspiration.

These tissue samples will be banked for the evaluation of PD-L1/PD-1, their associated immune suppressive pathways and other immune activation pathways to assess the effect of treatment upon the tumor microenvironment and the correlations between these immune parameters and clinical response. Immunohistochemistry, flow cytometry, quantitative PCR assays and microarray analysis will be employed. In addition, to identify potential mutated neoepitope-specific T-cell repertoire by TCR clonality and/or the MANAFEST assay and in pre- and post-treatment tumor specimens and peripheral blood lymphocyte (PBL) over time on treatment.

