9. STUDY SCHEDULE

Patients will be evaluated and consented at the time of initial diagnosis of LAPC. Patients should meet all eligibility criteria and complete all screening procedures prior to starting SOC chemotherapy, however they can be enrolled up to one month after initiating SOC chemotherapy to allow for time to gather all records from outside institutions if necessary. Patients will then receive 8-16 14-day cycles of FOLFIRINOX-based chemotherapy, followed by SBRT between 2-4 weeks after completion of chemotherapy. Both chemotherapy and radiation therapy are standard therapies for LAPC, and will be administered off-trial. They will have another evaluation for eligibility to receive immunotherapy after completion SBRT at which point they will be randomized during Phase II and they will initiate Cycle 1 Day 1 of combination immunotherapy within 2 weeks of completion of SBRT. The patient will undergo Post-Immunotherapy Evaluation within one week after Cycle 1 Day 28.

Pre-surgical Study Schedule						
Procedure	Screening/ Baseline	Pre-Immunotherapy Screening (within 3 weeks prior to C1D1)	Cycle 1 Immunotherapy (within 2 weeks after completion of SBRT)			End of Cycle 1 (day before surgery or C1D28, whichever is earlier) ²⁴
			C1D1 ²	C1D2 ³	C1D15 ⁴	
Visit Window ¹ (days)			-	-	+3	-3/+14
Nivolumab (All patients)			X			
GVAX (Phase 1 and Arm B patients)				X		
BMS-813160 (All patients) ⁵			X	X	X	X
Eligibility criteria	X	X				
Randomization (Phase 2 only) ⁶		X				
Demographics	X					
Medical History ⁷	X	X				
Medications	X	X	X		X	X
Physical Exam ⁸	X	X	X			X
Vital Signs and pulse ox ⁹		X	X	X	X	X
Height ⁹		X				
Weight		X	X		X	X
Performance Status	X	X	X		X	X
EKG for PR, QRS and QTcF ¹⁰		X	X		X	X
Hematology profile ^{11, 12}	X	X	X		X	X
Chemistry profile ^{11, 13}	X	X	X		X	X
TSH ^{11, 14}		X	X			X
Serum/Urine Preg ^{11, 15}	X	X	X			
CA 19-9 ¹¹	X	X	X			X
Urinalysis and microscopic exam ^{11, 16}		X				
INR ¹¹		X				
HLA-Typing ¹¹			X			
Adverse event evaluation		X	X		X	X
Vaccine Site Assessment						X
PET-CT, CT, or MRI ¹⁷	X	X				X ¹⁸
Tumor measurements ¹⁷	X	X				X ¹⁸
Pathology Review	X	X				
Peripheral blood for research (up to 100cc) ¹⁹			X			X
Serum (20cc) ¹⁹			X			X
Plasma (20cc) ¹⁹			X			X
Archival Tissue ²⁰	X					
EUS Core Biopsy ¹⁹		X ²¹				X ²²
QoL Questionnaire ²³			X			X

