20. Archival tissue from non-study biopsies may be collected at any time throughout the study.
21. Biopsy (4-6 cores) will be done during endoscopy for fiducial placement (not tied to pre-immunotherapy screening visit timing).
22. EUS Guided biopsy will be obtained for research purposes if subject is not a surgical candidate. If subject is a surgical or NanoKnife candidate, biopsy will be obtained intraoperatively during surgical resection. If metastases are noted, subjects will be offered a biopsy of metastases for research purposes.
23. QOL survey may be completed up to 3 days prior to a visit.
24. If End of Cycle 1 window overlaps with C1 D15 window, these visits may be combined.

A Phase I/II trial of combination immunotherapy with nivolumab and a CCR2/CCR5 dual antagonist (BMS-813160) with or without GVAX following chemotherapy and radiotherapy for locally advanced pancreatic ductal adenocarcinomas (PDACs)

Surgery should be scheduled to occur between five to seven weeks after completion of SBRT. If surgery is scheduled after completion of Cycle 1 (i.e. >28 days from nivolumab dosing), anti-CCR2/5 (BMS-813160) therapy will be continued up to the day before surgery. A second dose of nivolumab and GVAX will not be administered because this is not considered a new cycle. Standard surgical procedure will be determined by the operating surgeon. The surgical procedure is considered standard of care, but must be performed at Johns Hopkins Hospital.

Post-treatment biospecimens will be obtained the following ways:

- Surgical candidate found to have resectable tumor – resected specimen will be obtained intraoperatively
- Surgical candidate found to have unresectable tumor – research core biopsies will be obtained intraoperatively
- Non-surgical candidate – EUS-guided tumor biopsy
 - Note, if a patient is noted to have developed metastases that can be safely biopsied (as determined by our interventional radiology team), they will be offered biopsy of the metastases.

For those who undergo a surgery or NanoKnife procedure, immunotherapy will be initiated within 6 to 12 weeks of the procedure. For those who are not surgical candidates, the immunotherapy will not be held.

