12.4 Analysis of Primary Endpoint of Phase II - Immunologic Assessment

The evaluable populations for Phase II primary immunologic endpoint includes all subjects who completed one cycle of study combination immunotherapy.

CD8/OX40 and CD8/CD137 double staining will be performed by the sequential striping/staining multiplex IHC method of formalin-fixed, paraffin-embedded (FFPE) tissue slides,³⁵ and will be further developed into a more quantitative assay for endpoint analysis with the Perkin-Elmer-Vectra multiplex immunofluorescent staining method in the Tumor Microenvironment Core ([name]/[name]) of the Bloomberg-Kimmel Institute for Cancer Immunotherapy.

For each group, the rate of immune response will be estimated as the proportion of patients treated with nivolumab and a CCR2/CCR5 dual antagonist (BMS-813160) with or without GVAX who achieve immune response, defined as >80% increase of infiltration of CD8+CD137+ T cell density after the first immunotherapy cycle at the time of surgery or surgical evaluation if not a candidate) compared to baseline (prior to SBRT and after chemotherapy), together with the corresponding 95% confidence interval.

A Phase I/II trial of combination immunotherapy with nivolumab and a CCR2/CCR5 dual antagonist (BMS-813160) with or without GVAX following chemotherapy and radiotherapy for locally advanced pancreatic ductal adenocarcinomas (PDACs)

Furthermore, descriptive statistics for immune parameters in pretreatment tumor biopsy specimens and that in matched post-treatment tumor specimens will be computed. Percent change in the intratumoral immune parameters will be reported using descriptive statistics and displayed graphically. Comparison of primary immune parameters between pretreatment tumor biopsy specimens and matched post-treatment tumor specimens will be conducted using paired t-tests (or Wilcoxon signed rank tests if appropriate) and McNemar's tests for dichotomous or categorical variables, respectively.

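### For non-surgical patients the End of Cycle 1 biopsy window runs past the start of Cycle 2, so an Arm C specimen counted under the doublet can follow GVAX

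*Combined protocol and SAP*

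**What the plan says.** **Endpoint.** Sections 1.4.2 and 12.4 define immune response as a rise of more than 80% in CD8+CD137+ T-cell density from baseline to tissue taken "after the first immunotherapy cycle at the time of surgery or surgical evaluation if not a candidate". Section 12.4 makes every patient who completed one cycle evaluable.

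**Biopsy.** Section 9, footnote 22, states: "EUS Guided biopsy will be obtained for research purposes if subject is not a surgical candidate". Section 8.1 places this biopsy "after pre-surgical evaluation if the patient is not a surgical candidate" and gives no latest date. In the pre-surgical schedule it sits in the column headed "End of Cycle 1 (day before surgery or C1D28, whichever is earlier", with a visit window of -3/+14 days. The text above that table gives a shorter interval: "The patient will undergo Post-Immunotherapy Evaluation within one week after Cycle 1 Day 28".

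**Cycle 2.** Cycle 1 lasts 28 days (Section 1.7). Section 9 states: "For those who are not surgical candidates, the immunotherapy will not be held". Section 5.1 lets a cycle slip by up to one week, and the post-surgical schedule gives C2D1 a +7-day window. GVAX is given on Day 2 of a cycle.

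**Arm C.** Section 1.7 states: "Arm C patients will receive nivolumab and BMS-813160 for Cycle 1 (prior to surgery) and then nivolumab and GVAX for Cycles 2 and beyond". Section 12.2 counts these patients in Group 1, the doublet group, on the strength of their Cycle 1 regimen.

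**Surgical patients.** Sections 1.7, 4.1 and 9 withhold a second nivolumab or GVAX dose when surgery falls after Day 28. There is no matching statement for patients who have the EUS biopsy instead.

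**The concern.** The endpoint is meant to capture one cycle of the assigned regimen. The surgical path protects that with an explicit bar on further nivolumab and GVAX before the specimen. The non-surgical path does not: a single surgical evaluation leads to both the biopsy and Cycle 2, and the order of the two is not stated. Under Section 3.5, patients unresectable because of local progression may go straight to Cycle 2 without rescreening.

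A biopsy on Day 40, for example, would comply with the schedule table and be counted under Section 12.4, although a second nivolumab dose could already have been given. In Arm C the regimen itself changes at that point: GVAX enters and BMS-813160 is no longer scheduled. A response in such a specimen would be credited to nivolumab plus BMS-813160, which is not the exposure the tissue reflects. With 8 to 10 patients in Group 1, one such case is visible in the estimate.

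**Working it through.** **1. Inputs (C1D1 = Day 1)**
- Biopsy window in the schedule table: Day 28 - 3 = Day 25 to Day 28 + 14 = Day 42.
- One-week window in the Section 9 text: ends on Day 28 + 7 = Day 35.
- C2D1 (nivolumab): Day 29 nominal, Day 29 + 7 = Day 36 with the routine delay.
- C2D2 (GVAX): Day 30 to Day 37.

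**2. Overlap = last biopsy day - dosing day, not below 0**

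| Window ends | C2D1 | Days after nivolumab | Days after GVAX |
|---|---|---|---|
| Day 42 (table) | Day 29 | 42 - 29 = 13 | 42 - 30 = 12 |
| Day 42 (table) | Day 36 | 42 - 36 = 6 | 42 - 37 = 5 |
| Day 35 (text) | Day 29 | 35 - 29 = 6 | 35 - 30 = 5 |
| Day 35 (text) | Day 36 | 0 | 0 |

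The overlap exists in three of four combinations, and for every routine C2D1 date under the table.

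**3. Who crosses the GVAX line.** In Arm A a late specimen follows a second doublet cycle; in Phase I and Arm B, a second triplet cycle. Both depart from the endpoint's time point, but the regimen is unchanged. Only in Arm C does the regimen differ. Arm C is 3/8 = 37.5% to 5/10 = 50% of Group 1.

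Section 1.7 expects 30-40% resected, so 60-70% unresected. Applied to Arm C, that is 1.8 to 2.1 of 3 patients, or 3.0 to 3.5 of 5. These are upper bounds: some unresected patients have cores taken during surgery, and the figures suppose that every EUS biopsy is late.

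**4. Effect on the estimate.** One misattributed responder moves the Group 1 rate by 1/8 = 12.5 points or 1/10 = 10 points. Section 12.2 sets the rates of interest at 5% and 30%.

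**5. The plan's own probabilities.** Exact binomial tails reproduce all 30 cells of the Section 12.2 table to within 0.0006. For example, with n = 8 and a true rate of 0.05, P(at least 2) = 1 - 0.95^8 - 8 × 0.05 × 0.95^7 = 0.057, as stated.

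**6. Illustration only.** Suppose post-GVAX specimens respond at 30% and all others at 5%. The documents give neither as an estimate for this situation; they are the plan's two benchmark rates. With n = 8 and one affected specimen:
- P(0) = 0.70 × 0.95^7 = 0.489
- P(1) = 0.30 × 0.95^7 + 0.70 × 7 × 0.05 × 0.95^6 = 0.390
- P(at least 2) = 1 - 0.489 - 0.390, about 0.12 (0.122 unrounded), against 0.057 with none affected.

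The same calculation gives 0.217 with two affected. With n = 10 it gives 0.086 with none, 0.259 with two and 0.364 with three. The plan attaches no decision rule to two responders; this shows only how sensitive the group is.

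**The case against.** The best reply is that the documents already imply the order. The endpoint is tied to surgical evaluation after the first cycle. The biopsy belongs to the pre-surgical schedule, and Cycle 2 opens a separate schedule that follows surgical evaluation. The End of Cycle 1 column also marks BMS-813160 for all patients; since Arm C has none scheduled from Cycle 2, the visit presupposes that Cycle 2 has not begun. The +14 days apply to the whole visit, and footnote 22 ties intraoperative specimens to the same cell, so the width may be there for surgical scheduling. All of this stands as evidence of intent. It is not a rule: the window still admits a later specimen, and Section 12.4 would still count it.

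A reader might infer more than the documents support:
- *That both windows always overlap Cycle 2.* The one-week window does not if C2D1 is on Day 36, and that sentence does not name the biopsy.
- *That 60-70% of patients are affected.* That share is an upper bound across all arms, and the regimen changes only in Arm C.
- *That the with/without-GVAX distinction is lost.* Only Arm C specimens can cross it. The groups are analysed separately, no between-group test is planned, and Section 12.2 calls the Group 1 assessment preliminary.
- *That Section 2.3 shows GVAX would produce a response within the overlap.* The tissue there, "resected just two weeks following a single neoadjuvant dose of GVAX identified the formation of novel vaccine-induced" structures, came from a trial of GVAX with cyclophosphamide in resectable disease. This trial omits cyclophosphamide (Section 2.7), and the two-week interval is approached only by the 12-day extreme of a 5-to-12-day range.

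**Conclusion.** The point holds as a gap in the timing rule for the primary specimen and should be fixed. The schedule table permits a non-surgical biopsy 6 to 13 days after C2D1; the one-week text permits up to 6 days, or none. The two windows disagree, and neither is tied to Cycle 2 dosing. The main consequence is confined to Arm C, where one late responder shifts the Group 1 rate by 10 to 12.5 points. In the other arms a late specimen misses the endpoint's time point without changing the regimen measured.

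This rests on 28-day cycles, a routine Cycle 2 delay of at most 7 days, and the EUS biopsy sharing the window of its column. The documents show that a late specimen can occur, not that any has occurred or will. The number affected cannot be derived from them.

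**What to change.** **Schedule.** Reconcile Section 1.4.2, the Section 9 text, the End of Cycle 1 column with footnote 22, and Section 12.4. Give one window for the research biopsy in non-surgical patients, and state that the biopsy is scheduled before the first Cycle 2 dose. No change to dosing is involved.

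**Analysis.** In Section 12.4:
- Define the primary post-treatment specimen as one taken before any Cycle 2 study drug.
- Do not count Arm C specimens taken after Cycle 2 GVAX in Group 1.
- Report all later specimens, from any arm, in a sensitivity analysis.
- Apply the rule from recorded dose and biopsy dates, and fix it before response results are examined.

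Enrollment closed on December 19, 2022 (Section 1.7), so the schedule change reaches only patients who have yet to complete Cycle 1. The analysis rule covers everyone and is the more useful half.

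**Cost.** The text changes are small. The EUS scheduling window becomes tighter, and if an EUS slot comes late a specimen may be lost to the primary analysis, because Cycle 2 is not held. In groups of 8 to 10, each lost specimen matters; the sensitivity analysis keeps those data in view.

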10. MEASUREMENT OF EFFECT

10.1 Antitumor Effect – Solid Tumors

10.1.1 Definitions

Evaluable for toxicity. All subjects are evaluable for toxicity after receiving first dose of immunotherapy.

Evaluable for objective response. All patients who have received at least two doses of immunotherapy and have had their disease re-evaluated with imaging will be considered evaluable for response.

10.1.2 Methods for Evaluation of Measurable Disease

All measurements should be taken and recorded in metric notation using a ruler or calipers. All baseline evaluations should be performed as closely as possible to the beginning of treatment and never more than 4 weeks before the beginning of the treatment. Subjects will be evaluated for anti-tumor effect by follow-up imaging (pancreas protocol CT, CT Chest/Abd/Pelvis, PET-CT imaging, and/or non-contrast CT chest and MRI Abd/pelvis) as outlined above. All subsequent scans (post-treatment) will be compared to the same pretreatment CT, PET/CT, or MRI that was used prior to initiating of study treatment.

The same method of assessment and the same technique should be used to characterize each identified and reported lesion at baseline and during follow-up. Imaging-based evaluation is preferred to evaluation by clinical examination unless the lesion(s) being followed cannot be imaged but are assessable by clinical exam.

Conventional CT and MRI: This guideline has defined measurability of lesions on CT scan based on the assumption that CT slice thickness is 5 mm or less. If CT scans have slice thickness greater than 5 mm, the minimum size for a measurable lesion should be twice the slice thickness. MRI is also acceptable in certain situations (e.g. for body scans).

Use of MRI remains a complex issue. MRI has excellent contrast, spatial, and temporal resolution; however, there are many image acquisition variables involved in MRI, which greatly impact image quality, lesion conspicuity, and measurement. Furthermore, the availability of MRI is variable globally. As with CT, if an MRI is performed, the technical specifications of the scanning sequences used should be optimized for the evaluation of the type and site of disease. Furthermore, as with CT, the modality used at follow-up should be the same as was used at baseline and the lesions should be measured/assessed on the same pulse sequence. Ideally, the same type of scanner should be used and the image acquisition protocol should be followed

as closely as possible to prior scans. Body scans should be performed with breath-hold scanning techniques, if possible.

10.1.3 **Metastases free survival (MFS)**

MFS is defined as the duration of time from start of treatment to identification of distant metastases on imaging or death, whichever occurs first. Individuals will be censored at the date of the last scan if no event occurs.

10.1.4 **Overall Survival (OS)**

OS is defined as the duration of time from start of study treatment to time of death. Individuals will be censored at the date of the last scan if no event occurs.

10.1.5 **Local Progression-Free Survival (LPFS)**

LPFS is defined as the duration of time from start of treatment to time of first documented local progression or death, whichever occurs first. Individuals will be censored at the date of the last scan if no event occurs.

10.2 **Quality of Life**

Quality of life will be assessed using the European Organization for Research and Treatment in Cancer quality of life core cancer questionnaire with the pancreatic cancer module (EORTC QLQ-C30/PAN26, **Appendix D**). The EORTC QLQ-C30 is a multidimensional, 30-item questionnaire, which assesses five functional scales (physical, role, cognitive, emotional, and social), three symptom scales (fatigue, pain, and nausea/vomiting), a global health/QOL scale, as well as 6 single items.⁴³ The EORTC QLQ-PAN26 supplements the core questionnaire with 26 items specific for patients with pancreatic cancer.^{44, 45} These instruments have been validated in patients receiving treatment for metastatic and resected pancreatic cancer and are sensitive to identify treatment related changes in quality of life. We will offer subjects the option to complete their QoL questionnaires as an online REDCap survey within the 3 days prior to a visit or on paper the day of a visit. Patients who choose the online option will be sent a personalized link allowing their responses to be directly imported into our REDCap database. The REDCap database is HIPAA compliant and once survey responses are submitted, the link will no longer work and data will not be visible to the patients.

